11.3.3 Follow-up

Median follow-up assessments will be calculated using the Kaplan-Meier method reversing the censoring values (2). In addition, descriptive median and range will be calculated.

Table 11.3.3.1 Median FU for PFS

	Median	95% CI
Follow-up	X.X	X.X-X.X

Table 11.3.3.2 Descriptive median FU for PFS

	Median	Min	Max
Follow-up	X.X	X.X	X.X

Table 11.3.3.3 Median FU for OS

	Median	95% CI
Follow-up	X.X	X.X-X.X

Table 11.3.3.4 Descriptive median FU for OS

	Median	Min	Max
Follow-up	X.X	X.X	X.X

11.3.4 Multivariate analyses

Table 11.3.4.1 Multivariate analysis of PFS (Independent Review assessment and “Per Protocol Patients” population)

Analysis of Maximum Likelihood Estimates								
Variable Label	Variable values	DF	Parameter Estimate	Standard Error	Chi-Square	Pr > ChiSq	Hazard Ratio	95% Hazard Ratio Confidence Limits
			X.X	X.X	X.X	X.XXXX	X.X	X.X-X.X

List of covariates in section 6.2.2

Table 11.3.4.2 Multivariate analysis of PFS (Investigator assessment and “Per Protocol Patients” population)

Analysis of Maximum Likelihood Estimates								
Variable Label	Variable values	DF	Parameter Estimate	Standard Error	Chi-Square	Pr > ChiSq	Hazard Ratio	95% Hazard Ratio Confidence Limits
			X.X	X.X	X.X	X.XXXX	X.X	X.X-X.X

List of covariates in section 6.2.2

Table 11.3.4.3 Multivariate analysis of PFS (Independent Review assessment and “All Evaluable Patients” population)

Analysis of Maximum Likelihood Estimates								
Variable Label	Variable values	DF	Parameter Estimate	Standard Error	Chi-Square	Pr > ChiSq	Hazard Ratio	95% Hazard Ratio Confidence Limits
			X.X	X.X	X.X	X.XXXX	X.X	X.X-X.X

List of covariates in section 6.2.2

Table 11.3.4.4 Multivariate analysis of PFS (Investigator assessment and “All EvaluablePatients” population)

Analysis of Maximum Likelihood Estimates								
Variable Label	Variable values	DF	Parameter Estimate	Standard Error	Chi-Square	Pr > ChiSq	Hazard Ratio	95% Hazard Ratio Confidence Limits
			X.X	X.X	X.X	X.XXXX	X.X	X.X-X.X

List of covariates in section 6.2.2

Table 11.3.4.5 Multivariate analysis of PFS (Independent Review assessment and “All Treated Patients” population)

Analysis of Maximum Likelihood Estimates								
Variable Label	Variable values	DF	Parameter Estimate	Standard Error	Chi-Square	Pr > ChiSq	Hazard Ratio	95% Hazard Ratio Confidence Limits
			X.X	X.X	X.X	X.XXXX	X.X	X.X-X.X

List of covariates in section 6.2.2

Table 11.3.4.6 Multivariate analysis of PFS (Investigator assessment and “All Treated Patients” population)

Analysis of Maximum Likelihood Estimates								
Variable Label	Variable values	DF	Parameter Estimate	Standard Error	Chi-Square	Pr > ChiSq	Hazard Ratio	95% Hazard Ratio Confidence Limits
			X.X	X.X	X.X	X.XXXX	X.X	X.X-X.X

List of covariates in section 6.2.2

Table 11.3.4.7 Multivariate analysis of ORR (Independent Review assessment and “Per Protocol Patients” population)

Analysis of Maximum Likelihood Estimates								
Variable Label	Variable values	DF	Parameter Estimate	Standard Error	Chi-Square	Pr > ChiSq	Odds Ratio	95% Odds Ratio Confidence Limits
			X.X	X.X	X.X	X.XXXX	X.X	X.X-X.X

List of covariates in section 6.2.2

Table 11.3.4.8 Multivariate analysis of ORR (Investigator assessment and “Per Protocol Patients” population)

Analysis of Maximum Likelihood Estimates								
Variable Label	Variable values	DF	Parameter Estimate	Standard Error	Chi-Square	Pr > ChiSq	Odds Ratio	95% Odds Ratio Confidence Limits
			X.X	X.X	X.X	X.XXXX	X.X	X.X-X.X

List of covariates in section 6.2.2

Table 11.3.4.9 Multivariate analysis of ORR (Independent Review assessment and “All Evaluable Patients” population)

Analysis of Maximum Likelihood Estimates								
Variable Label	Variable values	DF	Parameter Estimate	Standard Error	Chi-Square	Pr > ChiSq	Odds Ratio	95% Odds Ratio Confidence Limits
			X.X	X.X	X.X	X.XXXX	X.X	X.X-X.X

List of covariates in section 6.2.2

Table 11.3.4.10 Multivariate analysis of ORR (Investigator assessment and “All Evaluable Patients” population)

Analysis of Maximum Likelihood Estimates								
Variable Label	Variable values	DF	Parameter Estimate	Standard Error	Chi-Square	Pr > ChiSq	Odds Ratio	95% Odds Ratio Confidence Limits
			X.X	X.X	X.X	X.XXXX	X.X	X.X-X.X

List of covariates in section 6.2.2

Table 11.3.4.11 Multivariate analysis of ORR (Independent Review assessment and “All Treated Patients” population)

Analysis of Maximum Likelihood Estimates								
Variable Label	Variable values	DF	Parameter Estimate	Standard Error	Chi-Square	Pr > ChiSq	Odds Ratio	95% Odds Ratio Confidence Limits
			X.X	X.X	X.X	X.XXXX	X.X	X.X-X.X

List of covariates in section 6.2.2

Table 11.3.4.12 Multivariate analysis of ORR (Investigator assessment and “All Treated Patients” population)

Analysis of Maximum Likelihood Estimates								
Variable Label	Variable values	DF	Parameter Estimate	Standard Error	Chi-Square	Pr > ChiSq	Odds Ratio	95% Odds Ratio Confidence Limits
			X.X	X.X	X.X	X.XXXX	X.X	X.X-X.X

List of covariates in section 6.2.2

Table 11.3.4.13 Multivariate analysis of OS (“Per Protocol Patients” population)

Analysis of Maximum Likelihood Estimates								
Variable Label	Variable values	DF	Parameter Estimate	Standard Error	Chi-Square	Pr > ChiSq	Hazard Ratio	95% Hazard Ratio Confidence Limits
			X.X	X.X	X.X	X.XXXX	X.X	X.X-X.X

List of covariates in section 6.2.2

Table 11.3.4.14 Multivariate analysis of OS (“All Evaluable Patients” population)

Analysis of Maximum Likelihood Estimates								
Variable Label	Variable values	DF	Parameter Estimate	Standard Error	Chi-Square	Pr > ChiSq	Hazard Ratio	95% Hazard Ratio Confidence Limits
			X.X	X.X	X.X	X.XXXX	X.X	X.X-X.X

List of covariates in section 6.2.2

Table 11.3.4.15 Multivariate analysis of OS (“All Treated Patients” population)

Analysis of Maximum Likelihood Estimates								
Variable Label	Variable values	DF	Parameter Estimate	Standard Error	Chi-Square	Pr > ChiSq	Hazard Ratio	95% Hazard Ratio Confidence Limits
			X.X	X.X	X.X	X.XXXX	X.X	X.X-X.X

List of covariates in section 6.2.2

11.3.5 Best reduction in sum of the product of the diameters lesions

Table 11.3.5.1 Best reduction in sum of product of diameters from baseline

SPD	N	Median	Mean	StD	Min	Max
	X	X.X	X.X	X.X	X.X	X.X

Waterfall plot (Figure 11.3.5.1) will be also shown for all patients with at one disease assessment after treatment.

11.3.6 Characteristics of responders

A summary of the main characteristics of patients showing clinical benefit, defined as patients with PR or better as best response or SD longer than 6 months assessed by Independent Review or by Investigators will be shown.

Listing 11.3.6.1 Characteristics of patients with clinical benefit.

Patient id.	Gender PS Age	Ann-Arbor stage	Bulky Lesion	Relapsed / Refractory	IPI	PAI	PIAI	No. of prior lines	Cycles received	Best response Lugano (IA)	Best response Lugano (IR)	Best PET SUV reduction (%)	PFS (IA)	DR (IA)	PFS (IR)	DR (IR)	OS

IR- Independent review IA- Investigator assessment

12 Safety Analysis

Safety analysis will be carried out on the “All Treated Patients” population.

12.1 Extent of exposure

12.1.1 Treatment administration

Table 12.1.1.1 Number of cycles administered and dose intensity

No. of cycles administered per patient	N	%
1	X	X.X
2		
3		
...		
Median (range)	X.X (X-X)	
Time on treatment (weeks)		
Median	X.X	
Range	X.X-X.X	
Plitidepsin cumulative dose (mg/m ²)		
Median	X.X	
Range	X.X-X.X	
Plitidepsin dose intensity (mg/m ² /wk)		
Median	X.X	
Range	X.X-X.X	
Plitidepsin relative dose intensity (%)		
Median	X.X	
Range	X.X-X.X	

12.1.2 Cycle delays

12.1.2.1 Number of patients and cycles with dosing delay, any relationship

Listing 12.1.2.1.1 Delays

Patient id.	Cycle	Day	Previous cycle	Previous cycle start date	Delayed cycle	Delayed cycle start date	Dose Delay calculated. (days)	Reason for dose delay	Dose Delay Spec.
							X		

Table 12.1.2.1.2 Number of patients and cycles with dosing delay, any relationship

	N	%
No. of patients treated	X	X.X
No. of patients susceptible to have a dosing delay*		
No. of patients with any dose delay**		
No. of cycles administered		
No. of cycles susceptible to be delayed***		
No. of cycles with dosing delay****		
No. of patients with		
No cycles delayed		
1 cycle delayed		
2 cycles delayed		
≥ 3 cycles delayed		

(*) All patients with more than one cycle. (**) Denominator = Number of patients susceptible to have a dosing delay

(***) All cycles excluding first cycle. (****) Denominator= Number of cycles susceptible to be delayed

Table 12.1.2.1.3 Number of patients and cycles with dosing delay according to the relationship

	Treatment-related		Non-treatment-related	
	N	%	N	%
No. of patients with *	X	X.X		
1 cycle delayed				
2 cycles delayed				
≥ 3 cycles delayed				
No. of cycles with dosing delay**				

(*) Denominator = Number of patients susceptible to have a dosing delay (**) Denominator= Number of cycles susceptible to be delayed.

Table 12.1.2.1.4 Length of dosing delay.

		Treatment-related		Non-treatment-related		Total	
Length of delay	Median (range)	N	%	N	%	N	%
Length of delay		N	%	N	%	N	%
≤ 7 days		X	X.X				
>7 days and ≤14 days							
> 14 days							

(*) Denominator= Number of cycles susceptible to be delayed.

Listing 12.1.2.1.5 Cycle delays due to AEs

Patient id.	Cycle	Delay reason according to Exposure form	Preferred term code	Adverse event reported (verbatim)	Grade	Relationship	Onset date	Resolved date	Significant consequences

AEs with action = 'Dose delayed' or 'Reduced and delayed'.

12.1.3 Dose omissions

Listing 12.1.3.1 Dose omissions

Patient id.	Cycle	Day	Cycle start date	Reason for dose omission	Dose omission Spec.

Table 12.1.3.2 Number of patients and cycles with dose omitted, any relationship

	N	%
No. of patients treated	X	X.X
No. of patients susceptible to have a dose omission *		
No. of patients with any dose omitted **		
No. of patients with **:		
No plitidepsin omissions		
1 cycle with plitidepsin dose omitted		
2 cycles with plitidepsin dose omitted		
≥ 3 cycles with plitidepsin dose omitted		
No. of cycles administered		
No. of cycles susceptible to have any dose omitted***		
No. of cycles with plitidepsin dosing omitted****		
No. of cycles with plitidepsin dosing omitted (treatment-related)		

(*) All patients with more than one infusion. (**) Denominator = Number of patients susceptible to have a dose omission

(***) All cycles excluding first cycle. (****) Denominator= Number of cycles susceptible to have a dose omission

NA: Not applicable

Table 12.1.3.3 Number of cycles with treatment-related dose omission by patient

	N	%
No. of patients with:	X	X.X
No omission		
1 cycle with treatment-related plitidepsin dose omitted		
2 cycles with treatment-related plitidepsin dose omitted		
≥ 3 cycles with treatment-related plitidepsin dose omitted		

Denominator= Number of patients that were on treatment on day 8 of cycle 1.

NA: Not applicable

Table 12.1.3.4 Reasons for dose omissions

Reasons for omissions	N	%
Treatment-related	X	X.X
Non-treatment-related		

NA: Not applicable

Listing 12.1.3.5 Dose omissions due to AEs

Patient id.	Cycle	Preferred term code	Adverse event reported (verbatim)	Grade	Relationship	Onset date	Resolved date	Significant consequences

AEs with action = ‘Dose skipped’ on day 8 or 15.

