## 7.4 CRITERIA FOR TREATMENT CONTINUATION

Patients can receive plitidepsin infusions (Day 1, 8, 15 of each cycle) for a maximum of six cycles (unless with PR or SD after Cycle 6: see Section [5.2.1.2](#)) if they fulfill the following requirements:

- ANC  $\geq 1.0 \times 10^9/L$ .
- Platelet count  $\geq 75 \times 10^9/L$ .
- Hemoglobin  $\geq 9.0$  g/dL.
- Calculated CrCL  $\geq 30$  mL/min (Cockcroft-Gault formula).
- Total bilirubin  $\leq 1.5 \times$  ULN ( $\leq$  grade 1).
- AST, ALT  $\leq 3.0 \times$  ULN ( $\leq$  grade 1).
- Normal value of electrolytes, including potassium, magnesium and calcium.
- Muscular toxicity (myalgia, muscular weakness, CPK increase)  $<$  grade 2.
- Other non-hematological drug-related AEs [except for increased gamma glutamyltransferase (GGT), not optimally treated nausea and vomiting, hypertension or alopecia]  $\leq$  grade 1.
- No clinically relevant ECG changes compared with grade at baseline.
- QTc must be  $\leq$  grade 1 before receiving the study treatment. In case of grade 1 QTc prolongation during treatment, and after discussion with the Sponsor, treatment must be continued with a normal value of electrolytes, including potassium, magnesium and calcium, being mandatory before the re-administration of plitidepsin.

- In case of QTc  $\geq$  grade 2, the study treatment must be discontinued, and the patient must be followed until recovery.

If these criteria are not met on Day 1 of any cycle after Cycle 1, the new cycle is to be delayed for up to two weeks until recovery. If these toxicities do not recover after a 2-week delay, the patient is to discontinue treatment and start the follow-up period unless there is obvious clinical benefit, in which case the patient might restart treatment at the Investigator’s discretion and after obtaining the approval of the Sponsor.

If these criteria are not met on Day 8 and 15 of any cycle (including Cycle 1), the scheduled infusion is to be omitted. Omitted doses for a given cycle are not to be recovered.

“Cycle delay”, therefore, is only applicable to the first infusion of a new cycle (i.e., Day 1) and not when an infusion takes place within the protocol-permitted window (one day) and not when treatment resumes after radiological assessment (see Section 5.10).

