## 7.5 DOSE REDUCTION

Dose adjustments are to be based on the worst toxicity occurring during the previous cycle. [Table 7](#) shows the plitidepsin dose levels used in this study.

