12.1.4 Dose reductions

All dose reductions should be considered and described, specifying the reason for reduction (drug related, non-drug related or other causes).

Listing 12.1.4.1 Dose reductions

Patient id.	Cycle	Day	Cycle start date	Previous dose	Reduced dose	Reason for dose reduction	Dose reduction Spec.

Table 12.1.4.2 Number of patients and cycles with dose reduction, any relationship

	N	%
No. of patients treated	X	X.X
No. of patients susceptible to have a dose reduced*		
No. of patients with any dose reduced**		
No. of patients with**:		
No plitidepsin reduction		
1 cycle with plitidepsin dose reduced		
2 cycles with plitidepsin dose reduced		
No. of cycles administered		
No. of cycles susceptible to have any dose reduced***		
No. of cycles with plitidepsin dose reduced ****		
No. of cycles with plitidepsin dose reduced (Treatment-related)		

(*) All patients with more than one infusion. (**) Denominator = Number of patients susceptible to have a dose reduced

(***) All cycles excluding first cycle of those patients who have only received the first infusion. (****) Denominator= Number of cycles susceptible to have a dose omission

NA: Not applicable

Table 12.1.4.3 Number of patients and cycles with dose reduction according to the relationship

Reasons for reductions	N	%
No. of cycles with dose reductions*		
Treatment-related	X	X.X
Non-treatment-related		

(* Denominator= Number of cycles susceptible to have a dose omission

NA: Not applicable

Listing 12.1.4.4 Dose reductions due to AEs

Patient id.	Cycle	Preferred term code	Adverse event reported (verbatim)	Grade	Relationship	Onset date	Resolved date	Significant consequences

AEs with action = 'Dose reduced/adjusted' or 'Reduced and delayed'.

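### The patient-level denominators for dose omissions, reductions and delays in SAP 12.1.2 to 12.1.4 do not match the points at which the protocol puts a patient at risk

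*SAP*

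**What the plan says.** SAP Appendix I sets a patient-level risk set for each type of dose modification.

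- **Omissions, any relationship (Table 12.1.3.2):** "All patients with more than one infusion. () Denominator = Number of patients susceptible to have a dose omission".
- **Omissions, treatment-related (Table 12.1.3.3):** "Denominator= Number of patients that were on treatment on day 8 of cycle 1".
- **Reductions (Table 12.1.4.2):** "All patients with more than one infusion. () Denominator = Number of patients susceptible to have a dose reduced".
- **Delays (Table 12.1.2.1.2):** "All patients with more than one cycle. () Denominator = Number of patients susceptible to have a dosing delay". At cycle level the footnotes read "All cycles excluding first cycle. () Denominator= Number of cycles susceptible to be delayed". The delay formula in SAP 8.2 subtracts the previous administration date from the current one, so it needs the later infusion to have been given.

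The protocol fixes when each modification can happen. Section 7.4 has the Day 8 or Day 15 infusion omitted when the continuation criteria are not met, and it expressly includes Cycle 1. For a Day 1 on hold it says: "If these toxicities do not recover after a 2-week delay, the patient is to discontinue treatment", with an exception for clear clinical benefit. Section 7.5 says: "Dose adjustments are to be based on the worst toxicity occurring during the previous cycle".

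Protocol 3.2 lists reductions, omitted doses and cycle delays due to treatment-related adverse events under the secondary safety endpoint.

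**The concern.** Each SAP denominator depends on how much drug the patient went on to receive. The protocol's risk points depend on the visit the patient had reached. The two differ for patients who stop early, and those include patients whose toxicity stopped treatment.

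An omission can occur at the second scheduled infusion, yet a second infusion must have been given before the patient counts as susceptible. A reduction cannot arise before Cycle 2 on the protocol's wording, yet patients who never reached Cycle 2 are in its denominator. A cycle put on hold and then abandoned leaves no later administration date, so the delay tables cannot contain it.

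What is at stake is how accurately tolerability is described. Early stops are realistic: in the previous phase II trial the non-cutaneous PTCL cohort had a median TTP/PFS of 1.6 months (Protocol Table 1), with grade 3/4 neutropenia, anemia and thrombocytopenia in 12%, 10% and 10% (Protocol 1.3).

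**Working it through.** The SAP tables are empty shells, so there is no planned rate to reproduce. All counts below are assumptions chosen to show direction and rough size. Only the 60 treated patients come from the documents (SAP section 2).

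**Assumed cohort.** Of 60 treated patients, 4 receive Day 1 only, have Day 8 and Day 15 omitted for toxicity, and stop after Cycle 2 is held and abandoned. The other 56 have more than one infusion; 20 of them have an omission. Of the 56, 44 start Cycle 2 and 12 stop before it is due. Among the 44, 11 have a reduction and 10 a delay.

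**1. Omissions.** Let N be the patients at risk on Day 8 of Cycle 1, k those with Day 8 and Day 15 omitted and no second infusion, and x the other patients with an omission. The rate that fits the protocol is (x + k)/N. The SAP denominator is N − k, and the footnote does not say whether the k patients stay in the numerator.

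- Numerator limited to susceptible patients: x/(N − k). This is below (x + k)/N whenever k > 0 and x + k < N.
- Numerator not limited: (x + k)/(N − k). This is above (x + k)/N whenever k > 0.

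With N = 60 and x = 20:

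| k | x/(N − k) | (x + k)/N | (x + k)/(N − k) |
|---|---|---|---|
| 1 | 20/59 = 33.9% | 21/60 = 35.0% | 21/59 = 35.6% |
| 3 | 20/57 = 35.1% | 23/60 = 38.3% | 23/57 = 40.4% |
| 4 | 20/56 = 35.7% | 24/60 = 40.0% | 24/56 = 42.9% |
| 6 | 20/54 = 37.0% | 26/60 = 43.3% | 26/54 = 48.1% |

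For k from 1 to 6 the error runs from 1.1 to 6.3 points too low on one reading, or 0.6 to 4.8 points too high on the other. With k = 0 there is none.

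**2. Reductions.** Let q be the patients with two or more infusions, all in Cycle 1. If no reduction occurs within Cycle 1, the rate among patients who reached a reduction point is x/(n − q), and the SAP gives x/n. The SAP rate is lower whenever q > 0 and x > 0. In the assumed cohort this is 11/56 = 19.6% against 11/44 = 25.0%. With other assumed counts (12 reduced, 57 with more than one infusion), the SAP rate is 12/57 = 21.1%. For q = 3, 6, 9 and 12 the alternative is 12/54 = 22.2%, 12/51 = 23.5%, 12/48 = 25.0% and 12/45 = 26.7%, a gap of 1.2 to 5.6 points.

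**3. Delays.** The SAP rate is 10/44 = 22.7%. The 4 patients whose Cycle 2 was held and abandoned are in neither numerator nor denominator. A separate row for them would read 4/48 = 8.3%, where 48 = 44 + 4 patients not discontinued before Cycle 2 was due. Counting them as delays would give 14/48 = 29.2%, but that changes what the table calls a delay.

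The denominator of the new row cannot be worded as patients on treatment on the due date. SAP 8.2 and Protocol 5.2.1.1 run treatment to 30 days after the last dose, barring death or new therapy. A patient who had one infusion and stopped would then still count on Day 29, and the denominator could reach 60: 4/60 = 6.7%.

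**The case against.** The strongest reply is that little is lost. Protocol 3.2 concerns modifications due to treatment-related events, and for omissions that is Table 12.1.3.3, whose denominator is sound. Table 12.2.1.1 reports events leading to delay, reduction and discontinuation in all treated patients, and SAP 7.1 adds a frequency table that includes skipped doses. Table 10.2.1 and Listing 10.2.3 show discontinuations due to adverse events. The omission listings are not limited to susceptible patients, and each summary table prints the number treated. All of this stands. It limits the harm, but it does not make Tables 12.1.3.2 and 12.1.3.3 agree.

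A held and abandoned Day 1 is also reported as a discontinuation, which is the outcome Protocol 7.4 prescribes. Leaving it out of the delay rate is therefore defensible, so the remedy is a separate row and not a new definition of delay.

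On reductions, Listing 12.1.4.1 has a column for the day, SAP 12.1.4 asks for all reductions to be considered, and its cycle-level footnote keeps Cycle 1 for patients with more than one infusion. The SAP may thus foresee reductions within Cycle 1. A denominator of Cycle 2 starters alone could then leave a real reduction outside its own risk set. That objection holds and shapes the fix.

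A reader might infer that all three rates are understated. The documents do not support that. The omission footnote leaves the numerator open, so that rate can err either way. A lower delay rate follows only if a cycle never given is counted as a delay. Nor is the row for delays over 14 days in Table 12.1.2.1.4 empty by construction: it will be sparse mainly because of the protocol's discontinuation rule, and restarts allowed for clinical benefit can still fill it.

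**Conclusion.** The point holds as a mismatch between the SAP's patient-level risk sets and the protocol. The omission denominator in Table 12.1.3.2 is wrong as written and disagrees with the adjacent table; the direction of its error depends on a numerator rule that the SAP does not state. The patient-level reduction rate is diluted if any patient has two or more infusions in Cycle 1 only and no reduction occurs within Cycle 1. The delay tables omit cycles held for toxicity and never given, which is a gap in reporting and not an error in the delay rate.

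The size is unknown. Errors of about 1 to 6 points arise under the assumed counts, and none arises if no such patients occur. These are descriptive safety tables with no test or decision rule, and the primary response analysis is unaffected.

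**What to change.** 1. **Table 12.1.3.2:** replace the patient-level denominator with that of Table 12.1.3.3, and state that numerator and denominator come from the same patients. Define being on treatment on Day 8 as not having discontinued before that day, because the 30-day convention would otherwise keep in patients who had already stopped.
2. **Table 12.1.4.2:** first reconcile the day column in Listing 12.1.4.1 with Protocol 7.5. Then use patients who started Cycle 2 as the patient-level denominator, and list separately any patient with a recorded reduction in Cycle 1.
3. **Tables 12.1.2.1.2 to 12.1.2.1.4:** keep the delay rate as it is. Add a row for patients whose next cycle was held for toxicity and not given, with patients not discontinued before the due date as its denominator. This depends on the data identifying such patients. The CRF is not among the documents, and SAP 8.2 names only a yes/no item for a delayed infusion, so this should be checked first.

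The cost is footnote wording and some programming. Reported modification rates may become slightly less favourable.
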